
Objectives:
 
Primary: The primary objective of this study is to evaluate occurrence of Adverse Events and their relationship to hMaxi-K following multiple intramuscular (IM) injections into the bladder wall. Two dose levels (16,000 µg and 24,000 µg by IM injection into the bladder wall) in females with moderate OAB/DO of ≥ six months duration are initially planned.
 
 • Treatment Emergent Adverse Events (TEAEs) – frequency and percentage of TEAEs, TEAEs by maximum severity and by relationship to study drug by treatment; summary of any AEs resulting in discontinuation of administration of study drug, serious adverse events (SAEs), and deaths during the study • Secondary: The secondary objectives of this study are to evaluate the following safety parameters: 
 – Clinical laboratory tests - changes and shift (whether the tests are within clinical normal range, whether they are clinically significant) from baseline by treatment – Electrocardiogram – change and shift from baseline (per ECG over-reader) by treatment – Vital Signs (systolic and diastolic blood pressure, and pulse rate) - change and shift from baseline 
The last assessment made prior to dosing of double-blind study drug will be used as the baseline for all analyses of these safety parameters.
 
In addition, efficacy parameters will be evaluated as change from baseline compared to placebo. Comparisons will be made between combined placebo (N = 6) vs. 16,000 µg (N = 6) and 24,000 µg (N = 6) active hMaxi-K group separately, and also between combined placebo and combined active group (N = 12), as well as between treatment comparisons for a dose response analysis. Efficacy evaluations will include the number of micturitions per day, volume per micturition, urgency episodes (1 or greater on urgency scale), and incontinence episodes from voiding diary, and pad weight. Efficacy evaluations will also include the following cystometric evaluations performed by the overreader at week 4 and 24: 1) Detrusor overactivity ≥ 5 cm H₂O (yes/no- INCLUSION CRITERIA); 2) Volume at first desire to void; 3) Detrusor pressure at beginning of voiding (prior to onset of first contraction, either volitional or involuntary); 4) Volume at first involuntary contraction; if detrusor overactivity (DO) present-Not applicable if no DO present; 5) Maximum detrusor pressure at FIRST contraction.
	

Post void residual (PVR) on bladder scan, and general and bladder specific quality of life assessments measured by participant evaluation using Kings Health Care Questionnaire (KHQ) and participant evaluation of response to treatment will also be evaluated.

Methodology:

This study is a double blind, placebo-controlled, multicenter, sequential active dose, Phase 1 study in females with moderate OAB/DO of \geq six months duration. The proposed study period is approximately 6 months following a single administration of study drug by multiple IM injections into the bladder wall per participant. The protocol sample size of this Phase I study is not intended to support the statistical significance of the primary endpoint as outlined in the study objectives. Rather, the sample size takes into account clinical safety considerations. Nine participants per dose level are planned: [6 assigned active treatment and 3 assigned placebo (PBS-20% sucrose only control group)]. Therefore a total of up to 9 participants will be enrolled in each dose group. Each arm of participants will be enrolled sequentially and enrollment into the next higher dose level will be dependent on assessment of safety. The participants chosen will be assigned in a randomized fashion to either placebo or an active treatment group within each group.

Number of subjects planned: Maximum of 18 participants.

Main criteria for inclusion:

The study population is women \geq 18 years old of non-child bearing potential with overactive bladder (OAB) and detrusor overactivity who are otherwise in good health.

The target population is women with idiopathic (non-neurogenic) OAB and detrusor overactivity (DO) who have been unable to tolerate, do not wish to continue, or have had unsuccessful results with, prior therapy for OAB/DO. OAB is characterized by a decreased bladder capacity, frequent voiding, frequent sensations of a strong urge to void, and in some participants, episodes of incontinence. DO is one or more uncontrolled phasic contraction(s) of the detrusor of at least 5 cm/H₂O pressure that are observed during urodynamic testing with or without urinary leakage.

Inclusion criteria will include clinical symptoms of overactive bladder of \geq 6 months duration including at least one of the following:

- a. Frequent micturition (\geq 8/24hrs)
- b. Symptoms of urinary urgency (the complaint of sudden compelling desire to pass urine, which is difficult to defer) or nocturia (the complaint of *waking* at night two or more times to void)
- c. Urge urinary incontinence (average of 5 per week – Urge urinary incontinence is defined as: the complaint of involuntary leakage accompanied by or immediately preceded by urgency)

Participants must also have a bladder scan at screening demonstrating a residual volume of \leq 200 mL and detrusor overactivity documented during baseline urodynamic testing of \geq 1 uncontrolled contraction(s) of the detrusor of at least 5 cm/H₂O.

Investigational product:

Treatment: hMaxi-K

Mode of Administration: Multiple intramuscular (IM) injections into the bladder wall during a single administration.

Duration of Treatment: The study will consist of up to a 14 day screening period prior to the single administration hMaxi-K on Day 0 (V2). A 6 month period for follow-up will complete the study for each participant. The total participation duration will be approximately 184 days; however each

participant on active treatment will be required to be followed for an additional 18 months (every 6 months) for safety evaluations only.

Comparator product:

Treatment: PBS-20% sucrose

Mode of Administration: Multiple intramuscular (IM) injections into the bladder wall.

Duration of Treatment: The study will consist of up to a 14 day screening period prior to the single administration PBS-20% sucrose placebo on Day 0 (V2). A 6 month period for follow-up will complete the study for each participant.

Criteria for evaluation:

Safety:

Safety will be assessed by analysis of adverse experiences (treatment emergent adverse events), clinical laboratory tests, electrocardiogram, and vital signs.

Efficacy:

Efficacy evaluations will include the number of micturitions per day, volume per micturition, urgency episodes and incontinence (or accident) episodes from voiding diary, and pad weight. Efficacy evaluations will also include the following cystometric evaluations performed by the site and/or the overreader at week 4 and 24: 1) Detrusor overactivity ≥ 5 cm H₂O (yes/no- INCLUSIONCRITERIA); 2) Volume at first desire to void; 3) Detrusor pressure at beginning of voiding (prior to onset of first contraction, either volitional or involuntary); 4) Volume at first involuntary contraction; if detrusor overactivity (DO) present-Not applicable if no DO present; 5) Maximum detrusor pressure at FIRST contraction.

PVR on bladder scan, and general and bladder specific quality of life assessments measured by participant evaluation using Kings Health Care Questionnaire (KHQ) and participant evaluation of response to treatment will also be evaluated.

Statistical methods:

Both the safety data and data to assess efficacy will be summarized using summary descriptive statistics by treatment group (combined placebo vs. 2 active treatment groups and combined placebo vs. combined treatment groups) and the total study population.

Linear mixed effect models will be used to estimate difference of changes from baseline between placebo and active treatment and to test whether there is dose-response for different outcomes. Generalized estimating equation (GEE) model will be used to estimate effects for the binary endpoints.

TABLE OF CONTENTS

STATISTICAL ANALYSIS PLAN	1
SIGNATURE PAGE	2
REVISIONS HISTORY LOG	2
SYNOPSIS.....	3
TABLE OF CONTENTS.....	6
LIST OF TABLES	8
1. LIST OF ABBREVIATIONS.....	9
2. INTRODUCTION	11
3. STUDY OBJECTIVES	12
3.1. Primary Objectives	12
3.2. Secondary Objectives	12
4. STUDY DESIGN	13
4.1. General Study Design and Plan	13
4.2. Study Population.....	13
4.2.1. Selection of Study Population.....	13
4.2.2. Subject Withdraw and Replacement.....	14
4.3. Randomization and Blinding.....	14
4.4. Study Assessments.....	14
4.4.1. Safety Assessment	19
4.4.2. Outcome Assessments	19
5. SAMPLE SIZE DETERMINATION	20
6. ANALYSIS POPULATIONS	21
7. GENERAL STATISTICAL CONSIDERATIONS.....	21
7.1. Interim Analyses and Data Monitoring	21
7.2. Multi-Center Studies.....	21
7.3. Multiple Comparisons / Multiplicity	21
7.4. Examination of Subgroups	21
7.5. Handling of Dropouts or Missing Data.....	21
7.6. Outlier Handling	21

7.7.	Adjustments for Covariates	21

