Statistical Analysis	Both the safety data and data to assess activity will be analyzed using summary descriptive statistics for the four cohorts and the total study population. The group sample sizes of 6 per arm achieve 80% power to detect a 30% reduction in frequency of voiding to placebo assuming a standard deviation of 2.5 with a significance level of 0.05 using a two-sided, two sample t-test. A comparison to baseline will also be done using a two-sided t- test. Total number of active treatment participants (N=12) will also be compared to total number of placebo participants (N=6).

Table 1. Procedures By Visit

Phase	Screening Phase			Post-Treatment Follow up Visits						
	Visit 1	Visit 1A ⁿ	Visit 2	Telephone Follow-up ^j	Visit 3	Visit 4	Visit 5	Visit 6	Visit 7	Visit 8
Day	-14	-14 to -8	0 (Baseline)	Day 1 & 3	8	15	29	57	85	169 (Final)
Week	-2		0	0	1	2	4	8	12	24
Visit Window (days)		+2	+2	Day 3±1	+2	+2	±2	±3	±5	±5
Signed Informed Consent	▲									
Evaluation of Inclusion /Exclusion Criteria	▲	▲	▲ ^f							
Demographics and Medical/ Surgical History	▲									
Physical Examination	▲		▲ ^f		▲	▲	▲	▲	▲	▲
ECG	▲		▲ ^a		▲		▲			▲
Previous / Concomitant Medication Assessment	▲	▲	▲ ^f		▲	▲	▲	▲	▲	▲
Vital Signs ^b	▲		▲ ^{f,l}		▲	▲	▲	▲	▲	▲
Objective OAB /DO Evaluation (Cystometry) ^b		▲ ^d					▲			▲
Bladder scan ^c	▲					▲		▲		▲
Dispense Daily Voiding Diary/Urgency questionnaire ⁱ	▲	▲	▲ ^f		▲	▲	▲	▲	▲	
Pad Test ^m		▲	▲		▲	▲	▲	▲	▲	▲
QoL (King’s Health Questionnaire) and SF-12			▲ ^f				▲	▲	▲	▲
Subjective Evaluation of Disease State ^k			▲ ^f		▲	▲	▲	▲	▲	▲
Subjective Evaluation of Response to Treatment ^k					▲	▲	▲	▲	▲	▲
ICIQ-SF			▲ ^f				▲	▲	▲	▲
Urinalysis and Urine Cultures ^d	▲	▲	▲ ^f		▲	▲	▲		▲	▲
Hematology Laboratory Tests ^e	▲		▲		▲	▲	▲		▲	▲
Chemistry Laboratory Tests ^e	▲				▲	▲	▲		▲	▲
Pharmacokinetic Assessment (urine and blood hSlo cDNA)			▲ ^{f,g}		▲	▲	▲	▲	▲	▲ ^g
Adverse Event Assessment		▲	▲ ^f	▲ ^j	▲	▲	▲	▲	▲	▲
Study Drug administered			▲							

- a. ECG will be done prior to administration of study drug and at 2 hours post dosing.

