5.1 Test Material and Administration

5.2 Study Medication

hMaxi-K is a double stranded naked plasmid DNA molecule carrying the human cDNA encoding the gene for the α , or pore forming, subunit of the human smooth muscle Maxi-K channel, *hSlo*. Expression of the *hSlo* gene is under control of the CMV promoter positioned upstream of the transgene and the construct also contains the Bovine Growth Hormone poly A site.

hMaxi-K is manufactured by Althea Technologies, Inc under GMP conditions. Sterile borosilicate vials of *hMaxi-K*, 2 ml, will be shipped to Sharp Clinical Services, Inc. (Phoenixville, PA) and stored at -20°C . Identical vials of 2 ml sterile PBS-20% sucrose manufactured by Olympia Compounding Pharmacy (Orlando, FL) will be shipped to Sharp Clinical Services, Inc. and stored at -20°C .

The table below provides information on the 16,000 μg and 24,000 μg doses of *hMaxi-K*. Each 2 mL vial contains 4000 μg per mL, so multiple vials will be used for each dosing event. The sites will store the vials in a locked freezer until use. Participant vials will be retained at the site until

the drug accounting processes have been completed, when they will either be returned to the Sponsor or destroyed with Sponsor approval.

Table 6. Final Dose-*h*Maxi-k

h Maxi-K Dose	16,000mcg	PBS-20% sucrose	24,000 mcg	PBS-20% sucrose
Volume	4 mL		6 mL	
Number of Vials	2		3	
Final Volume	4 mL		6 mL	
Number of IM injections	20 injections of 0.2 ml at specified sites in bladder wall approx. 1 cm apart		30 injections of 0.2 ml at specified sites in bladder wall approx. 1 cm apart	

Note: In each dose cohort 6 participants will receive *h*Maxi-K and 3 will receive PBS-20% sucrose (placebo).

Sharp Clinical Services, Inc. will maintain a randomization schedule generated by a Statistical Group (Section 5.3.1). Following notification by the site that an eligible participant is to be randomized, Sharp Clinical Services, Inc. will ship a sequentially labeled study drug participant kit following the central randomization schedule by overnight mail on ice within one to seven days prior to the planned treatment date. The sites will store the participant kit at -20°C in a locked freezer prior to use. Vials can be kept at -20°C for up to 360 days. Participant kits will be retained at the site until study completion when they will either be returned to the sponsor or destroyed.

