If there is a single site, then Sharp will be allowed to ship all kits to that site to be distributed by the site's local pharmacy in a sequential fashion. Prior to dosing each participant, the site will confirm which kit number they will be using with the clinical research monitor to minimize errors.

If a kit is damaged, a replacement kit will be made available. Prior to using a replacement kit (which will be shipped to the site from Einstein where will it be stored), the site will contact the clinical research monitor for directive as to which replacement kit they can use as a substitute for a damaged kit. The replacement kit number will be provided by the **unblinded** statistician. If there is an additional site included, then the drug supply may be shipped to Einstein from the single site, where it will be stored and distributed in a sequential and blinded fashion to the sites by overnight mail on ice within one to seven days prior to the planned treatment date.

The individual participants' double blind patient drug kit will contain a two-part (tear-off) label. The duplicate portion of this label will be detached and affixed to a label page (to be retrieved at study close out by Ion Channel Innovations designated monitor) at the time of randomization and test drug administration. There will be central randomization. The sites will be instructed to call the Sponsor or designee for the assigned subject number after each participant's screening visit allowing ample time prior to Visit 2 for shipment of the drug.

The duplicate label from each patient drug kit will be affixed to a separate log in the source documents at Visit 2.

The double-blind patient drug kit is to be given to the participant will be supplied as indicated above and labeled with tear-off labels containing the following information:

- Study ION-03 OAB
- Subject identification number (kit number)

- Contains two or three 2 mL sterile borosilicate vials (each vial contains either 4000 µg per mL *hMaxi-K* or PBS-20% sucrose placebo)
- INSTRUCTIONS: Inject 0.2 mL of study drug into the bladder wall (as directed at 20 sites for Cohort 1 and at 30 sites for Cohort 2) approximately 1 cm apart.
- Store kit at -20° C in a locked freezer prior to use. Store at controlled room temperature once thawed: 15° C to 30° C (59° F to 86° F).
- CAUTION: New Drug – Limited by Federal Law (or United States) to investigational use.
Ion Channel Innovations, LLC
[name]
[name]

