10.4 Analysis of Endpoints

The methods described in this section will be updated during the course of the study. The final version of the statistical analysis plan (SAP) will be issued before the treatment code is broken.

This double blind, phase 1 study is designed to evaluate the safety of a single bladder injections of 2 different doses of *hMaxi-K* in individual participants. Both the safety data and data to assess efficacy will be analyzed using summary descriptive statistics for the two cohorts and the total study population. Associations between study therapy and the outcomes will be assessed using-repeated measures analyses, and explored in multivariate models, as needed.

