10.1. Adverse Events

Safety summaries will include the incidence of treatment-emergent adverse events (TEAEs), which are defined as any event that began on or after the date of the first treatment dose or worsened in severity or frequency after treatment dose was initiated. Events worsening in severity will be considered new AEs. AEs recorded on the CRF that began prior to treatment and did not worsen in severity will be recorded as medical history will not be included in the AE summary tables and data listings. Any AEs happens in long-term safety follow-up will be reported in a separate listings and not included in the main planned analyses.

All TEAEs will be coded using version 17.1 of Medical Dictionary for Regulatory Activities (MedDRA) and summaries will present data by System Organ Class (SOC) and preferred term (PT).

The following conventions will be followed in summarizing multiple occurrences of an adverse event for a certain assessment period when summarizing data from individual participant:

- Each subject will be counted only once within a body system (SOC) or a preferred term;
- The highest known severity within a body system or a preferred term will be assigned to the event;
- The strongest relationship within a body system or a preferred term will be assigned to the event.

The denominator used for calculation of the percentages will be the number of subjects in the Safety population per treatment.

Specifically, TEAEs will be summarized in the Safety Population. An overall summary of TEAEs, including number of subjects in population, number of subjects with one or more TEAEs, number of participants with one or more Serious TEAEs, number of deaths (if any), and number of subjects experiencing AEs resulting in discontinuation, will be presented in Table 14.3.1.1 by treatment group. The frequency and percentage of AEs by SOC and PT for each treatment group will be presented in Table 14.3.1.2.

The frequency and percentage of AEs related to study drug (Possibly Related, Probably Related, and Definitely Related) by treatment group will be displayed by treatment in Table 14.3.2.

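### The dose-specific adverse-event comparisons use one pooled placebo group, although placebo is 20 injections in Cohort 1 and 30 in Cohort 2; show placebo by cohort as well

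*SAP*

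**What the plan says.** **Grouping of safety data.** The statistical methods paragraph of the SAP synopsis covers both safety and efficacy data and sets the groups as "combined placebo vs. 2 active treatment groups and combined placebo vs. combined treatment groups". SAP 10.1 follows this for AEs: "The frequency and percentage of AEs by SOC and PT for each treatment group will be presented in Table 14.3.1.2", and "The denominator used for calculation of the percentages will be the number of subjects in the Safety population per treatment". Tables 14.3.1.1 and 14.3.2 are also by treatment group. No split of placebo by cohort is described.

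**The placebo procedure.** Protocol 5.2 (Study Medication), Table 6, gives the lower dose as "20 injections of 0.2 ml at specified sites in bladder wall approx. 1 cm apart", and the higher dose as 30 injections of the same volume. The kit, which holds either active drug or placebo, carries one instruction for both: inject "as directed at 20 sites for Cohort 1 and at 30 sites for Cohort 2". The same section says that the matched total volume of 4 mL or 6 mL keeps the blind. Protocol 5.3.1 and SAP 4.3 randomise 6 active to 3 placebo within each dose group, and the cohorts are enrolled one after the other.

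**Number of groups.** The protocol synopsis promises "summary descriptive statistics for the four cohorts and the total study population". Protocol 10.4 promises "summary descriptive statistics for the two cohorts and the total study population". SAP section 14 declares no change from the protocol.

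**The concern.** The primary objective is the occurrence of AEs and their relationship to hMaxi-K, compared with placebo. The randomised, procedure-matched comparison for each dose is with the three placebo participants of the same cohort. Pooling replaces them with six, of whom three had a different number of punctures and a different injected volume.

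Injection number can plausibly matter for AEs. One stopping rule in Protocol 5.2.1 sets aside bladder pain or irritation that the investigator attributes to acute trauma from cystoscopy, the bladder muscle injections or catheterisation. The causality scale in Protocol 9.4 names the participant's condition, other therapies and accident as alternative causes, but not the injection procedure. An event caused by the needle could therefore be rated as possibly related and be counted in Table 14.3.2.

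At stake is how the two dose columns are read. A needle effect would make 16,000 µg look safer than placebo and 24,000 µg look less safe. The protocol says that further doses may be added depending on the safety and efficacy results.

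**Working it through.** **1. Reproduce the dosing table.** Inputs from Protocol 5.2: 0.2 mL per injection and 4000 µg/mL.

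- Cohort 1: 20 × 0.2 mL = 4 mL; 4 × 4000 = 16,000 µg.
- Cohort 2: 30 × 0.2 mL = 6 mL; 6 × 4000 = 24,000 µg.

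Both agree with Table 6. The concentration is fixed, so dose and injection number rise together by a factor of 1.5.

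**2. Injection mix of the pooled control.** Three placebo participants with 20 injections and three with 30 give a mean of (3×20 + 3×30)/6 = 25. The active arms have 20 and 30.

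**3. Expected AE proportions if the drug is inert.** Assumption, because the documents give no rate: each injection independently carries a risk p of causing an AE, with p from 0.5% to 3%. The risk after k injections is 1 − (1 − p)^k, and the pooled placebo risk is the mean of the two.

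| p | 20 injections | 30 injections | Pooled placebo | 16,000 µg minus pooled | 24,000 µg minus pooled |
|---|---|---|---|---|---|
| 0.5% | 9.5% | 14.0% | 11.7% | −2.2 | +2.2 |
| 1% | 18.2% | 26.0% | 22.1% | −3.9 | +3.9 |
| 2% | 33.2% | 45.5% | 39.3% | −6.1 | +6.1 |
| 3% | 45.6% | 59.9% | 52.8% | −7.1 | +7.1 |

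Differences are in percentage points. If risk were instead proportional to injection number, the false difference would be larger. With a 20-injection risk of 20%, 40% or 60%, the 30-injection risk is 30%, 60% or 90%, pooled placebo is 25%, 50% or 75%, and the differences are ±5, ±10 and ±15 points.

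**4. Same-cohort placebo.** Active and placebo have the same injection number, so the expected difference for an inert drug is 0 in each cohort, whatever p is.

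**5. Combined active against combined placebo.** Active is (6a + 6b)/12 and placebo is (3a + 3b)/6, where a and b are the 20- and 30-injection risks. Both equal (a + b)/2, so the bias is 0 at the planned allocation. Replacements (up to 3 per dose) could disturb this. With 9 active in Cohort 1 instead of 6, and a = 0.2, b = 0.3, the combined active risk is (9×0.2 + 6×0.3)/15 = 0.24 against 0.25, a difference of −1 point. Across the unbalanced allocations tried (9:3 or 6:6 in one cohort; risks 0.2/0.3 and 0.4/0.6), it is about 1 to 3 points in size.

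**6. Total error of the two controls.** This is the root-mean-square error of the dose-minus-placebo difference for an inert drug, with bias included, in the scenarios of step 3. For 16,000 µg:

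- Own-cohort placebo: √[a(1−a)(1/6 + 1/3)].
- Pooled placebo: √[a(1−a)/6 + (3a(1−a) + 3b(1−b))/36 + ((b−a)/2)²].

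For 24,000 µg, exchange a and b.

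| p | 16,000 µg, own | 16,000 µg, pooled | 24,000 µg, own | 24,000 µg, pooled |
|---|---|---|---|---|
| 0.5% | 0.21 | 0.18 | 0.25 | 0.19 |
| 1% | 0.27 | 0.23 | 0.31 | 0.25 |
| 2% | 0.33 | 0.28 | 0.35 | 0.29 |
| 3% | 0.35 | 0.30 | 0.35 | 0.29 |

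Pooled placebo has the smaller total error in all eight comparisons. Own-cohort placebo removes the bias but costs more in precision than it gains.

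**The case against.** **Pooling is a reasonable choice with 18 participants.** This stands in part. Pooled placebo has the lower total error in every scenario above, and the protocol itself plans pooled comparisons: total active (N=12) against total placebo (N=6) in its synopsis, and the pool of placebo participants for bladder capacity in section 10.3. It argues for keeping the pooled columns and against a rule that each dose be read first against its own-cohort placebo. It does not argue against showing the split.

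**The matched columns could hardly separate needle from drug.** This also stands. Comparing 3 with 3, the 30-injection placebo group shows more affected participants with probability 28% to 49% and fewer with probability 17% to 23% in these scenarios. The columns are descriptive only.

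**The information is available elsewhere.** SAP 8.4 lists dosing by participant and SAP 10.1 lists every AE by participant, so the split can be rebuilt by hand. The DSMB also reviews unblinded safety data after each cohort (Protocol 5.2.2). No described AE summary shows the split, however.

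**The columns are inferred.** SAP 10.1 does not define treatment group. The pooled reading comes from the SAP synopsis, and the table shells are a companion document not supplied here. They may already show placebo by cohort.

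**Readings that go too far.** A reader might infer that pooling makes an inert drug look dose-related. The documents do not support that. The 24,000 minus 16,000 µg difference, +4 to +14 points in these scenarios, involves no placebo. It follows from the fixed concentration and would be the same with any placebo columns. A reader might also take the four cohorts of the protocol synopsis to mean each dose with its own placebo. That fits two doses by two arms, but the synopsis does not define the term.

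**Conclusion.** The point holds as a cheap improvement to the AE tables, not as an error that invalidates them. Each dose-specific AE comparison in the SAP uses a control group of which half had a different injection number and belonged to the other cohort. If AE risk rises with injection number, the expected false difference for an inert drug is about 2 to 7 points, negative at 16,000 µg and positive at 24,000 µg.

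That size rests on an assumed risk of 0.5% to 3% per injection, equal and independent across injections. It would be zero if AEs came only from what both cohorts share, such as cystoscopy, catheterisation and local anaesthesia. It is small beside the sampling error of six participants per group. The combined active against combined placebo contrast is unaffected at the planned 6:3 allocation.

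The confounding of dose with injection number is built into the design. What the plan lacks is an AE summary that shows the procedure-matched placebo, the group that could inform on it. The mismatch between four and two cohorts in the protocol is a separate wording conflict that needs settling in any case.

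**What to change.** - In SAP Tables 14.3.1.1, 14.3.1.2 and 14.3.2, add descriptive columns for 20-injection placebo (n=3) and 30-injection placebo (n=3), each beside the active group of the same cohort. Keep the pooled columns.
- Define treatment group in SAP 10.1 so that the columns are explicit.
- Add a table note that dose and injection number rise together, so an AE difference between 24,000 and 16,000 µg cannot be attributed to the drug alone.
- Do not prescribe that own-cohort placebo is read first.
- Reconcile the four cohorts of the protocol synopsis with the two of Protocol 10.4.

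The cost is SAP wording and two extra columns in three tables. No new data are needed and no planned output is lost. The downside is that the by-cohort placebo columns hold three participants each and are imprecise.
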